7.7.6 Safety data

Analyses will be done on Safety Set.

7.7.6.1 Analysis set and grouping for the analyses

The overall observation period will be divided into three mutually exclusive segments:

- pre-treatment period: from day of patient's informed consent to the day before first dose of study medication except for patients who started their study medication 12 months or less prior to enrollment. For these patients, the pre-treatment period will include any day before the first dose of study medication.
- on-treatment period: from day of first dose of study medication to 30 days after last dose of study medication
- post-treatment period: starting at day 30+1 after last dose of study medication

7.7.6.2 Adverse events (AEs)

Summary tables for adverse events (AEs) have to include only AEs that started or worsened during the on-treatment period, the treatment-emergent AEs. However, all safety data (including those from the pre and post-treatment periods) will be listed and those collected during the pre-treatment and post-treatment period are to be flagged (also tabulated for posttreatment period).

The incidence of treatment-emergent adverse events will be summarized by system organ class and or preferred term, severity (mild/moderate/severe), type of adverse event and relation to study treatment. A table will be also provided for incidence of treatment-emergent adverse events per total patient-years exposure.

Deaths reportable as SAEs and non-fatal serious adverse events will be listed by patient and tabulated by preferred term.

Additionally, AEs with suspected relationship to study drug, requiring dose adjustment, leading to drug interruption/discontinuation will be specifically tabulated and listed, as well as cardiac AEs of special interest ("Sudden cardiac death", "Cardiac arrhythmias", "Congestive heart failure", "Cardiomyopathy", "Pulmonary hypertension").

The number of adverse events adjusted by time of exposure (events per year or events per month) will also be tabulated.

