The enrollment is defined as the patient's entry into the study; which is the point at which informed consent form is signed. Data will be collected on a minimum of 40 eligible pediatric patients who signed informed consent. These patients should be aged ≥ 10 to <18 years at enrollment, are diagnosed with non-transfusion dependent thalassemia and require to be treated with deferasirox or started deferasirox treatment 12 months or less prior to enrollment. These patients will be followed for up to 5 years from the start of deferasirox treatment. Retrospective data collection will be done for patients whom have started deferasirox 12 months or less prior to enrollment.

The baseline is defined as the timeframe before the patient starts treatment with deferasirox.

In patients who have protocol specified assessments performed prior to the date of first deferasirox treatment, the baseline data will be collected if it is within the following timeframe prior to the date of starting deferasirox treatment (see also table 7-2):

- 1.5 months for all laboratory assessments
- 6 months for vital signs, weight, height, LIC, ECG, ECHO, CMR, ocular and audiometry assessments
- 12 months for pubertal assessments (Tanner stage).

Post baseline data will be collected from the start date of deferasirox and then on for five years.

Investigational treatment

Deferasirox dispersible tablets

Deferasirox dispersible tablet is currently marketed in three dosing strengths (125, 250, 500 mg) and is dosed based on body weight. The currently approved dose range is up to 40 mg/kg/day.

Deferasirox dispersible tablets prescribed by physicians in actual practice setting will be used in accordance with the local label.

Initial deferasirox dose 10 mg/kg/d, 7 d/wk in accordance with the deferasirox prescribing information. Dose titration of deferasirox may be performed based on LIC levels as measured by magnetic resonance imaging (MRI) and/or SF levels and safety markers in steps of 5–10 mg/kg/d as defined by local label requirements.

Deferasirox Film Coated Tablets (FCTs)

Because of the chronic nature of chelation therapy and the importance of patient compliance, an improved deferasirox formulation for oral administration has been developed.

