7.5 Study size

This is a non-interventional study which plans to enroll a minimum of 40 patients. No formal sample size calculation based on the primary endpoint of long-term safety is performed.

Protocols for observational studies (or registry studies) to assess the natural history of a disease or to evaluate the safety of an established product (investigational drug) may not include formal sample size calculations. Data on global epidemiology of NTDT are scarce, see Section 7.2. Also the prevalence of NTDT patients with clinically significant iron overload constitutes a very small percentage of total number of NTDT patients.

Given the small prevalence of the disease under consideration, data on the 40 patients would provide relevant data as described by the computation of probabilities to detect adverse events as shown below. Statistical computations were performed (see table below) to evaluate probabilities to detect at least one patient with an AE given 40 patients and different scenarios of AE incidence rates (Hanley and Lippman-Hand 1983). This table shows a reasonable chance to detect adverse events occurring with an incidence of 5% or higher.

Probability to observe at least one AE for different incidence rates:

Incidence rate of an adverse event	Probability that at least one patient out of 40 experiences the adverse event
3%	0.70
4%	0.80
5%	0.87
6%	0.92
10%	0.99

Incidence rate of an adverse event	Probability that at least one patient out of 40 experiences the adverse event
15%	1.00

7.6 **Data management**

Data will be entered routinely into the study database by the physician/study coordinator.

Novartis personnel (or designated CRO) will review the data entered by investigational staff for completeness and accuracy.

Page 44

Electronic data queries stating the nature of the problem and requesting clarification will be created for all other discrepancies and missing values and sent to the investigational site via the EDC system. Designated physician site staff is required to respond promptly to queries and to make any necessary changes to the data.

Concomitant treatments entered into the database will be coded using the WHO Drug Reference List, which employs the Anatomical Therapeutic Chemical classification system. Medical history/current medical conditions, cause of death and adverse events will be coded using the Medical dictionary for regulatory activities (MedDRA) terminology.

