7.7.4.2 Statistical hypothesis, model, and method of analysis

Counts and frequencies of patients with any drug related SAEs will be provided descriptively on Safety Set overall and by preferred term and system organ class.

In case of high number of SAEs, exposure-adjusted adverse event incidence will also be tabulated.

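### Section 7.7.6.2 sets total patient-years as the denominator of a treatment-emergent AE incidence table without defining the numerator; if patients are counted, the first-event rate is understated

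*Protocol*

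**What the plan says.** Protocol section 7.7.6.2 plans three summaries of treatment-emergent adverse events:

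- a crude incidence summary by system organ class or preferred term, severity, type of event and relation to treatment;
- an exposure-adjusted table: "A table will be also provided for incidence of treatment-emergent adverse events per total patient-years exposure";
- an event rate: "The number of adverse events adjusted by time of exposure (events per year or events per month) will also be tabulated".

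The second summary has a stated denominator and no stated numerator. Section 7.7.3 lists total patient-years of exposure as one cohort-level exposure summary. Stopping a patient's time at the first event is mentioned nowhere.

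Follow-up is long: "These patients will be followed for up to 5 years from the start of deferasirox treatment" (section 7.1). Events count as treatment-emergent within the window that section 7.7.6.1 defines: "on-treatment period: from day of first dose of study medication to 30 days after last dose of study medication".

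For the primary endpoint, section 7.7.4.2 gives counts and frequencies of patients with drug-related SAEs and adds: "In case of high number of SAEs, exposure-adjusted adverse event incidence will also be tabulated". That sentence gives neither a numerator nor a denominator.

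**The concern.** Once a patient has had a first event of a given type, that patient can add nothing further to a count of patients with at least one event. Total exposure nevertheless goes on accumulating the patient's remaining time, up to 5 years here. The quotient is then not the rate of first events among patients still at risk. It is lower, and the gap widens as the event becomes commoner or starts earlier. Even with an unchanging hazard, the figure drifts down as follow-up lengthens.

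In a study meant to describe long-term safety, a reader could take such a figure as a yearly first-event rate and conclude that common events are rarer per year of treatment than they are.

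**Working it through.** **The plan's own figures.** The protocol states no exposure-adjusted rate. Its only AE computation is the detection table in section 7.5, and 1 − (1 − p)^40 reproduces it: 0.704, 0.805, 0.872, 0.916, 0.985 and 0.999, against the printed 0.70, 0.80, 0.87, 0.92, 0.99 and 1.00. That table is sound and does not bear on this point.

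**Which numerator?** The sentence just before the exposure-adjusted table uses the term incidence for the summary by class, severity and relation, which is conventionally a count of patients. The section's last sentence covers the number of events over exposure time and presents this as an additional table. If the exposure-adjusted table also counted events, the section would ask for the same quantity twice. Patients is therefore the more natural reading, but it is an inference.

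**Formula if patients are counted.** Let p be the 5-year risk, T = 5 years of exposure for all, and λ = −ln(1 − p)/T a constant hazard.

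- Rate on total exposure: p/T.
- Mean time to first event or end of exposure: (1 − e^(−λT))/λ = p/λ.
- Rate on time to first event: p ÷ (p/λ) = λ.
- Ratio of the two rates: p/(λT) = p/(−ln(1 − p)).

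For early onset, suppose all first events are spread evenly over the first 6 months. Mean time at risk is 5(1 − p) + 0.25p, so the shortfall is 1 − [5(1 − p) + 0.25p]/5 = 0.95p.

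Every value of p below is an assumption.

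| 5-year risk p | Patients per 100 total PY | First events per 100 PY at risk (constant hazard) | Shortfall, constant hazard | Shortfall, early onset |
|---|---|---|---|---|
| 5% | 1.00 | 1.03 | 2.5% | 4.8% |
| 10% | 2.00 | 2.11 | 5% | 9.5% |
| 20% | 4.00 | 4.46 | 10% | 19% |
| 30% | 6.00 | 7.13 | 16% | 28.5% |
| 50% | 10.0 | 13.9 | 28% | 47.5% |
| 80% | 16.0 | 32.2 | 50% | 76% |

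**Incomplete follow-up.** At p = 50% under a constant hazard, the shortfall is 26% with 10% dropout per year. It is about 20% if exposure is spread uniformly over 0.5 to 5 years.

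**Drift with follow-up.** At p = 50%, λ = 0.1386 per year. The rate on total exposure is 1 − e^(−0.1386) = 12.9 per 100 PY after 1 year and 10.0 after 5 years, although the hazard stays at 13.9 throughout.

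**If events are counted.** Take a recurrent rate of 0.20 per year over 5 years. Expected events are 1.0 per patient, so events over total exposure give 1.0/5 = 0.20, which is correct. Patients over total exposure give (1 − e^(−1))/5 = 0.126. The bias therefore depends wholly on the numerator.

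**The case against.** The main objection is that the numerator is inferred. The protocol never says that this table counts patients with at least one event, and if it counts events, total exposure is the right denominator. The Amendment 1 log records the event-rate sentence as an addition, so its overlap with the existing table may be accidental. This stands as a limit on the claim. It does not remove the need for a change: on the other reading two tables give the same quantity, one of them labelled incidence, and no first-event rate is planned.

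It can also be said that table definitions belong in the SAP, which is not shown. That holds for the numerator. The denominator, however, is fixed in the protocol, and a SAP that stopped time at the first event would depart from that text.

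The size is modest for uncommon events. With a minimum of 40 patients, a 20% risk means 8 patients, and the exact Poisson 95% interval of about 3.5 to 15.8 dwarfs a 10% shortfall. This stands for events of that frequency. At 50%, about 20 patients have the event and the relative standard error is near 1/√20 = 22%, so a 28% systematic shortfall is no longer negligible.

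Finally, the first-event rate also depends on follow-up when the hazard is not constant. With 50% risk and all onsets in the first 6 months, it falls from 0.5/(0.125 + 0.5) = 0.80 per year at 1 year to 0.5/(0.125 + 2.5) = 0.19 at 5 years, a fall of 76%. On total exposure it falls from 0.50 to 0.10, or 80%. The proposed denominator therefore removes the post-event time but does not make early-onset rates comparable across different lengths of follow-up.

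**Conclusion.** The point holds conditionally. If the section 7.7.6.2 table counts patients, as it most naturally reads, the first-event rate is understated by 1 − p/(−ln(1 − p)) under a constant hazard and full 5-year exposure, and by more for early-onset events. The shortfall is small for events with a 5-year risk below about 10% (at most about 10% even with early onset) and substantial for events that affect about half of patients or more. If the table counts events, there is no bias, only duplication and a misleading label.

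A reader might infer three stronger things that the protocol does not support:

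- **That the primary SAE analysis is affected.** The primary variable is a plain proportion of patients. The conditional sentence in section 7.7.4.2 defines neither numerator nor denominator, so it cannot be taken to use the same measure.
- **That AE rates in general will be strongly understated.** The crude incidence and the event rate are both planned and free of this bias, and the larger percentages rest on assumed frequencies.
- **That a planned comparison will be distorted.** No AE comparison between age groups or with other studies is planned. The historical comparison in section 7.7.5.3 concerns weight, height and BMI.

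**What to change.** In section 7.7.6.2, define exposure-adjusted incidence as the number of patients with at least one event divided by summed exposure to the first event, or to the end of the on-treatment period for patients without one, computed separately for each system organ class and preferred term. Keep events over total exposure as a second table, labelled an event rate. If the conditional exposure-adjusted incidence in section 7.7.4.2 is meant to count patients, use the same definition there; if it is meant to count events, say so.

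The cost is a sentence or two and a changed denominator in the table program. AE start dates and dosing dates are already collected (section 9), so no new data are needed. There are two drawbacks: the denominator will differ from row to row, and the table needs a note that the rate still depends on length of follow-up when the hazard is not constant.

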7.7.6.3 Laboratory abnormalities

All laboratory values will be converted into SI units and the severity grade calculated using the low/normal/high classifications based on laboratory normal ranges and for selected parameters by notable/extended ranges (see Table 7-3 below).

The following summaries will be generated separately for hematology, biochemistry and urinary laboratory tests:

- shift tables using normal/notable/extended ranges to compare baseline to the worst ontreatment value.
- listing of all laboratory data with values flagged to show the corresponding normal/notable/extended ranges.

For each hematology/iron metabolism parameter, observed values (and changes from baseline) will be summarized by descriptive statistics (n, mean, standard deviation, minimum, lower quartile, median, upper quartile and maximum).

Creatinine clearance estimated using the Schwarz formula for patients < 18 years old and Cockcroft-Gault formula for patients ≥ 18 years old will be displayed using relative change from baseline by categories.

Similar to adverse events, the number of events related to lab abnormalities adjusted by time of exposure (events per year or events per month) will be tabulated.

Table 7-3	Criteria for clinically	notable and extended	laboratory ranges
1 abic 1 -5	Officeria for Chilicany	, iiotabie alia extellaca	iaboratory ranges

Parameter	Criteria
ALT/AST	>5×ULN and >2×baseline value (extended range >10×ULN and >2×baseline value)
Serum creatinine	>33% increase from baseline and >ULN at two consecutive measurements at least 7 days apart
Creatinine clearance	<60 mL/min at two consecutive measurements at least 7 days apart (extended range <40 mL/min)

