Non-interventional study (NIS)' in this context is used synonymously with 'observational study', i.e., does not involve any kind of intervention, experimental or otherwise. In these studies, interviews, questionnaires and blood samples may be performed as normal clinical practice.

6 Research question and objectives

This observational study will evaluate the long term safety of deferasirox therapy in pediatric patients ≥ 10 to ≤ 18 years at enrollment with NTDT in actual practice setting.

Table 6-1 Objectives and Endpoints

Objectives	Endpoints	Analysis
Primary		
Evaluate the long term safety of deferasirox	Proportion of patients having SAEs that are considered to be related to study drug up to 5 years from the start of deferasirox treatment	Section 7.7.4
Secondary		

Evaluate the incidence of serum creatinine and SGPT (ALT) increases in actual practice setting	The proportion of patients having (up to 5 years from the start of deferasirox treatment): Serum creatinine > 33 % above baseline and above the age adjusted ULN in at least two consecutive post-baseline measurements at least 7 days apart from each other. SGPT (ALT) above 5 x ULN in at least two consecutive post-baseline measurements at least 7 days apart from each other	Section 7.7.5.1
Evaluate renal and hepatic safety parameters over time	Absolute/relative changes from baseline of SGPT (ALT), SGOT (AST), total bilirubin, alkaline phosphatase, serum creatinine, creatinine clearance quarterly up to 5 years. Proportion of patients having hepatic and renal clinical events that are considered to be related to study drug up to 5 years from the start of deferasirox.	Section 7.7.5.2
Evaluate growth by gender	Absolute change in BMI, weight and height from baseline to EOS Proportion of patients falling behind in growth based on height, weight and BMI	Section 7.7.5.3
Evaluate sexual development by gender	Mean age at assessment for each Tanner stage Changes from baseline to the last on-study value of all Tanner stage parameters.	Section 7.7.5.4
Evaluate long term efficacy of deferasirox as measured by serum ferritin and LIC	Absolute/relative change in SF and LIC from baseline to EOS Proportion of patient achieving a SF <300 ng/mL Proportion of patients achieving LIC <3 mg Fe/g dw Proportion of patients reinitiating deferasirox after discontinuation due to a "stopping rule" *	Section 7.7.5.5

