All local laboratories contributing to the study should provide the sponsor with a copy of the laboratory's certification and a tabulation of the normal ranges and standard deviations from control values for each of the parameters being evaluated. These laboratory references should be forwarded to the sponsor prior to study start and updated promptly if any information changes during the course of the study.

Data on the following parameters will be collected when available:

- serum creatinine
- creatinine clearance (the method used by the site to check the creatinine clearance will also be collected)
- serum ferritin

- urea
- SGOT (AST)
- SGPT (ALT)
- alkaline phosphatase
- bilirubin
- proteinuria (the method used by the site to check the proteinuria will also be collected)

Renal biopsy

Information on renal biopsies will be collected when available.

Cardiac parameters

Information on blood pressure, pulse, ECG, echocardiography and CMR will be collected when available.

Information on cardiac events that meet the definition of Serious Adverse Event must be reported as described in Section 9.

A list of cardiac events potentially related to cardiac iron overload is provided below:

- Sudden cardiac death
- Cardiac arrhythmias
- Congestive heart failure
- Cardiomyopathy
- Pulmonary hypertension

Liver iron concentration

Information on LIC and the method of its assessment will be collected when available.

Auditory and ophthalmology

The Prescribing Information recommends annual audiometry and ophthalmology examinations. The examination dates and findings (normal or not) will be collected on the audiometry and ophthalmology eCRF. Information about the examination must be present in the source documentation at the study site. Findings that meet the definition of an adverse event must also be recorded in the AE eCRF.

Transfusion requirements

Blood transfusion requirements will be collected if available.

7.4 **Data sources**

Initiation of the participating sites will be performed by Novartis and/or a designated CRO. Before study initiation, a Novartis representative (or designee) will review the protocol and eCRF with the physicians and their staff.

Sites enrolling patients in this study will record data on eCRFs provided by Novartis (or designee) which will capture, check, store and analyze the data.

CROs (if utilized) will follow their own internal SOPs that have been reviewed and approved by Novartis.

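### Creatinine clearance changes formula at age 18, so patients who turn 18 on study have a Cockcroft-Gault value compared with a Schwartz baseline, which adds a step unrelated to kidney function

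*Protocol*

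**What the plan says.** - **Formula and measure of change (Section 7.7.6.3).** For creatinine clearance: "Schwarz formula for patients < 18 years old and Cockcroft-Gault formula for patients ≥ 18 years old will be displayed using relative change", taken against baseline and shown in categories.
- **Age at entry (Section 7.1).** "These patients should be aged ≥ 10 to <18 years at enrollment".
- **Follow-up (Section 7.1).** "These patients will be followed for up to 5 years from the start of deferasirox treatment". Treatment may have begun before enrollment: "Retrospective data collection will be done for patients whom have started deferasirox 12 months or less prior to enrollment".
- **Baseline (Section 7.1).** "The baseline is defined as the timeframe before the patient starts treatment with deferasirox".
- **Secondary endpoint (Table 6-1).** "Absolute/relative changes from baseline of SGPT (ALT), SGOT (AST), total bilirubin, alkaline phosphatase, serum creatinine, creatinine clearance quarterly up to 5 years". Section 7.7.5.2 summarizes these values and their changes by quarter.
- **Notable range (Table 7-3).** Clearance "<60 mL/min at two consecutive measurements at least 7 days apart (extended range <40 mL/min"). One pair of limits serves all ages.
- **Collected data (Section 7.3, laboratory evaluations).** "creatinine clearance (the method used by the site to check the creatinine clearance will also be collected").
- **Monitoring text (Section 7.1).** For adults it names Cockcroft-Gault or MDRD, and for children Schwartz. Section 7.7.6.3 names only Cockcroft-Gault for adults.

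No section recomputes the baseline with the adult formula, keeps one formula per patient, or separates values obtained after the 18th birthday.

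**The concern.** A change from baseline is interpretable only if both values are measured the same way. Here the formula depends on age, and the study population ages across the cut. The two formulas use different inputs: height and creatinine for Schwartz; age, weight, sex and creatinine for Cockcroft-Gault. A patient with stable kidneys can therefore move to another relative-change category at the 18th birthday.

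Renal parameters over time are a named secondary objective, and the study exists to describe exposure up to 5 years. The switch falls in the later part of follow-up, where a slow change in clearance would be looked for. The analysis is descriptive, so no model or test would absorb the step; the display is the result.

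**Working it through.** The protocol gives no figure on this point. Its only design calculation, the chance of seeing at least one event in 40 patients (Section 7.5), reproduces as 1 - (1 - p)^40, for example 0.871 at 5% against the stated 0.87. It has no bearing here.

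**Step 1: which formula applies to baseline.** Enrollment is below 18 and baseline precedes the first dose, so in practice every baseline is a Schwartz value. (A patient enrolled just before 18 who starts treatment after the birthday could be a rare exception.) If the adult clause referred to age at enrollment, it would apply to nobody. It has effect only as age at assessment.

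**Step 2: how many patients cross 18.** Inputs from the protocol: at least 20 patients aged 10 to ≤12, at least 20 aged >12 to <18, and up to 5 years from treatment start. Assumption: ages are even within each stratum.

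- Treatment starts at enrollment, full follow-up: those older than 13 cross. (18 - 13)/(18 - 12) = 0.833; 20 × 0.833 = 16.7 of 40 (42%). None of the younger stratum crosses.
- All started 12 months before enrollment: (18 - 14)/6 × 20 = 13.3 (33%).
- If ≤12 means completed years, so that the older stratum runs from 13 to 18: 20 of 40 (50%).
- Dropout at a constant rate, cumulative d by year 5, h = -ln(1 - d)/5: expected number = (20/6) × d/h. For d = 30%, (20/6) × 4.21 = 14.0 (35%). For d = 50%, (20/6) × 3.61 = 12.0 (30%).
- Only 2 years of follow-up: 20 × 2/6 = 6.7 (17%).

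With full follow-up, mean time after 18 in the older stratum is 12.5/6 = 2.08 years. Over both strata that is 2.08/10 = 21% of patient-time. With 50% dropout it is 18.5%.

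**Step 3: size of the step.** Assumed standard forms: Schwartz = k × height/creatinine; Cockcroft-Gault = (140 - age) × weight/(72 × creatinine), times 0.85 if female. On the same sample at age 18:

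ratio = [122 × weight × (0.85 if female)/72] / (k × height)

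Creatinine cancels. The protocol gives no k, height or weight, so these are assumptions.

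| Patient | k = 0.413 | k = 0.55 | k = 0.70 |
|---|---|---|---|
| Male 150 cm, 40 kg | +9% | -18% | -35% |
| Male 155 cm, 42 kg | +11% | -17% | -34% |
| Male 165 cm, 50 kg | +24% | -7% | -27% |
| Male 175 cm, 65 kg | +52% | +14% | -10% |
| Female 150 cm, 40 kg | -7% | -30% | not used |
| Female 155 cm, 45 kg | +1% | -24% | not used |
| Female 175 cm, 65 kg | +30% | -3% | not used |

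Worked example, male 165 cm, 50 kg: 122 × 50/72 = 84.7; 0.55 × 165 = 90.75; 84.7/90.75 = 0.93, or -7%.

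**Step 4: can the step alone trigger the <60 mL/min flag?** With the largest fall (-35%, ratio 0.6455), the Schwartz value would have to be below 60/0.6455 = 93 mL/min already. At an assumed creatinine of 0.6 mg/dL, a male of 165 cm, 52 kg has 146.9 by Cockcroft-Gault against 113.6, 151.3 or 192.5 by Schwartz. A female of 155 cm, 45 kg has 108.0 against 106.7 or 142.1. A male of 155 cm, 42 kg has 118.6 against 142.1 (k = 0.55) or 180.8 (k = 0.70). None comes near the limit.

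**The case against.** **The comparison is inferred.** Section 7.7.6.3 does not say in words that an adult-formula value is divided by a Schwartz baseline, and Section 7.7 leaves further details to the SAP, which could recompute the baseline. This stands in part: a SAP can repair the rule. But the protocol itself joins the age-based formula to relative change from baseline, and a SAP that follows the text as written inherits the mismatch.

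**The main measures do not use the formula.** The primary variable is drug-related SAEs. The renal incidence endpoint is serum creatinine more than 33% above baseline and above the age-adjusted ULN, at two consecutive measurements. Serum creatinine is also summarized by quarter, and all laboratory data are listed. This stands in full. A reader might infer that the switch could create or hide the study's renal signal. The documents do not support that, because unchanged serum creatinine beside a jump in clearance would expose the artefact.

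**The <60 and <40 mL/min flags.** A reader might also infer that these are corrupted. The limits do apply across both formulas, and the protocol does not say whether either value is indexed to body surface area. However, none of the worked examples approaches 60, so an effect on the flags is possible but not shown.

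**The size rests on assumptions.** Body size and k drive both direction and magnitude, and some steps are close to zero. The share crossing 18 depends on an age distribution that the protocol does not give, and patients who permanently stop deferasirox other than under the stopping rule are withdrawn. This also stands, so only ranges can be given.

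**Age-appropriate formulas match the monitoring text in Section 7.1.** That supports using each formula to describe a patient's current level. It does not support mixing them within one change from baseline.

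**Conclusion.** The point holds as a fault in one derivation rule. Applied as written, the rule sets Cockcroft-Gault values against Schwartz baselines for every patient who is assessed after turning 18. That is roughly 12 to 20 of 40 patients if ages are even within strata, and fewer with short follow-up. The artificial step has no single direction: about -35% to +52% in males and -30% to +30% in females over the assumed body sizes and constants.

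The relative-change categories in Section 7.7.6.3 are affected directly. The quarterly clearance summaries in Section 7.7.5.2 are affected if they use the same derived variable. Section 7.7.5.2 names no formula; site-reported values that followed the monitoring text would switch at adulthood too, possibly to MDRD. The damage is confined to descriptive clearance displays in the later years.

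**What to change.** 1. For all change-from-baseline and category displays of creatinine clearance, use one formula per patient throughout. Compute Schwartz centrally wherever height and creatinine are both available.
2. Pre-specify a single Schwartz constant that does not change within a patient. Otherwise the fault returns: moving from 0.55 to 0.70 alone is a step of 0.70/0.55 - 1 = 27%.
3. Show Cockcroft-Gault values at 18 or over in a separate display, and never compare them with a Schwartz baseline.
4. State that Section 7.7.5.2 uses the same derived variable, and reconcile Sections 7.1 and 7.7.6.3 on the adult formula.

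With one formula and one constant, the step from switching is 0% by construction. The cost is derivation wording and programming, with no new data collection. There are two drawbacks. Schwartz is carried somewhat beyond age 18. And, because no visit schedule is imposed, height may not accompany every creatinine value, so some clearances will be missing.
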